4. OBJECTIVE(S)/SPECIFIC AIMS AND HYPOTHESES

- *A concise statement of the goal(s) of the current study.*
- *The rationale for and specific objectives of the study.*
- *The goals and the hypothesis to be tested should be stated.*

OBJECTIVES	ENDPOINTS	JUSTIFICATION FOR ENDPOINTS
Primary		
To Compare the efficacy of two different modes of administration of peripheral nerve block for postoperative pain control after primary ACL reconstruction.	Pain control as measured by a visual analogue scale (0-10) on post operative day 1,2,3,4,7, and at first follow up visit (Day 14).	Our study seeks to better clarify the effectiveness of two postoperative pain control methods after ACL reconstruction. Visual analogue scale is commonly used to assess pain in postoperative patients. This is an easy way to assess patients pain in a quick and easy to understand method.
Secondary		
To compare the daily opioid consumption in patients post operatively after ACL Reconstruction.	This will be measured as daily consumption of oxycodone (morphine equivalents) on post operative day 1,2,3,4,7, and 14.	A secondary objective of our study would be to examine pain control objectively by opioid consumption each day. This is a secondary measure of the efficacy of pain control. The hope is that with better pain control via peripheral nerve block patients would be less reliant on opioid pain medication.
To determine the effectiveness of pain control and quality of sleep.	We will measure this by asking if they had a disturbance in their sleep or trouble getting to sleep through email surveys.	Our study wants to look at how pain control and sleep quality are correlated and to analyze if better pain control also allowed patients to have better postoperative sleep habits.

General Well Being	Short Form - 12 Survey given preoperatively and at 14 days post operatively.	This assessment test is to classify changes in general health and wellbeing, physical, and mental health.
Knee Assessment Score	International Knee Documentation Committee Subjective Knee Form (IKDC) to be given preoperatively and at 14 days post operatively.	Designed to assess patients with a variety of knee disorders.

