8. NUMBER OF SUBJECTS

- *Indicate the total number of subjects to be accrued locally. If applicable, distinguish between the number of subjects who are expected to be pre-screened, enrolled (consent obtained), randomized and complete the research procedures.*
- *If your study includes different cohorts, include the total number of subjects in each cohort.*
- *If this is multisite study, include total number of subjects across all sites.*

We will enroll 78 patients in the event that we lose some to follow up or if patients decide to unenroll in the study. We don't foresee many patients being lost to follow up because all patients will be enrolled only until their first follow up visit. The historic rate of patient's not following up with the surgeons after ACL reconstruction is almost 0.

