12. STATISTICAL ANALYSIS

- *Describe how your data will be used to test the hypotheses.*
- *State clearly what variables will be tested and what statistical tests will be used.*

- *Include sample size calculations.*
- *If this is a pilot study, state which variables will be examined for hypothesis generation in later studies.*

Blinding:

Due to the nature of the intervention (bolus block, continuous infusion pump), it is not possible to blind the physicians or patients.

Consent:

Consent will be obtained during the preoperative visit, prior to surgery.

Randomization:

Subjects will be randomly assigned in a 1:1 ratio to either bolus block or continuous catheter. The randomization will be stratified by hospital (Plainview, Franklin, Huntington, Long Island Jewish, or North Shore University Hospital).

The Biostatistics Unit will develop a randomization procedure using a permuted block design within the Biostatistics Randomization Management System (BRMS).

Additional details of the procedure, including required record keeping, will be further developed upon approval of this protocol. The Biostatistics Unit has extensive experience in implementing and in producing detailed documentation for such procedures.

Intention to Treat (ITT):

All analyses will be carried out according to the ITT principle. The ITT population will be all subjects randomized, regardless of what treatment they actually received. All patients will be analyzed in the group to which they were randomized.

Statistical Considerations:**Specific Aims:**

To compare the efficacy of two postoperative pain control methods (bolus block, continuous catheter) in patients undergoing ACL reconstruction.

Primary Outcome

Outcomes measured on post-operative days 0, 1,2,3,4,7, and at the post-operative follow-up visit. (Outcomes for days 0, 1,2,3,4, and 7 will be obtained via email and electronic surveys . Outcomes for the post-operative follow-up visit will be measured during the postoperative visit which takes place between days 10 and 14. This will be referred to as "Day 10").

- Pain Control

- Maximum pain will be measured on a scale of 0 to 10, where 0 represents no pain and 10 represents the worst possible pain. Patients will report the maximum pain felt in the 24 hours
- Current pain will be measured on a scale of 0 to 10, where 0 represents no pain and 10 represents the worst possible pain.
- Daily opioid consumption (expressed as morphine equivalents).

Secondary Outcomes

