Outcomes measured on post-operative days 1,2,3,4,7, and at the post-operative follow-up visit.

- Quality of Sleep
 - Trouble falling asleep due to pain (yes,no)
 - Wake due to pain (yes,no)

Outcomes measured at post-operative follow-up visit

- Satisfaction with surgery, on a scale of 0 to 10, where 0 represents extremely dissatisfied and 10 extremely satisfied
- Adverse events: Adverse events will be assessed at each visit. At the end of the study, each subject will be categorized as having had one or more adverse events, or not having had any adverse events.
- Serious Adverse events: Serious adverse events will be assessed at each visit and via telephone on post-operative day 1, 2, 3, 4 and 7. At the end of the study each subject will be categorized as having had one or more serious adverse events, or not having had any serious adverse events.

Statistical Methods:

Primary Outcomes:

For each outcome, repeated measures analysis of variance (RMANOVA), where post-operative pain control method (bolus block, continuous catheter) is the between subjects effect and post-operative day is the within subjects effect will be used to examine the association between pain control method and that outcome. Site (stratification variable) will be included as a covariate in each model. The interaction of post-operative control method and day will be included in the model. If the interaction is significant, then pairwise comparisons of pain control method at each day will be carried out within the RMANOVA model. If the usual assumptions required for the ANOVA model are not met, then a suitable transformation, or an appropriate non-parametric method will be used.

Secondary Outcomes:

For binary outcomes measured on days 1,2,3,4,7 and 10:

For each outcome, a generalized linear mixed model (GLMM) for binary clustered (i.e., hierarchical) data will be used to examine the association between pain control method and that outcome. GLMM will be used to account for the hierarchical structure of the data, (namely, multiple days within a subject). Site (stratification variable) will be included as a covariate in each model.

For binary outcomes measured on day 10 only:

For each outcome, logistic regression will be used to examine the association between pain control method and that outcome. Site (stratification variable) will be included as a covariate in each model.

For satisfaction with surgery:

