Analysis of variance (ANOVA) will be used to examine the association between pain control method and satisfaction with surgery. Site will be included as a covariate in the model. If the usual assumptions required for the ANOVA model are not met, then a suitable transformation, or an appropriate non-parametric method will be used.

Sample Size Justification:

In a published study of 85 patients undergoing arthroscopic shoulder surgery, patients were randomly assigned to catheter (43 patients) or single-shot block (42 patients) for postoperative analgesia. Median pain with movement on day 3, measured on a visual analog pain scale, 6 in the single-shot group and 4 in the catheter group. As there is limited information available regarding postoperative pain levels following ACL reconstruction, we will assume that the difference in pain levels between bolus block and continuous catheter will be similar (i.e. continuous catheter will be 2 points lower than bolus block). The standard deviation will be estimated as 2.5. This estimate was obtained by dividing the range (10-0) by 4.

The proposed analysis will examine pain levels over multiple days during the postoperative period. If a significant interaction between treatment and day is found, it will be of interest to determine which days differ. Although this comparison will be carried out within the ANOVA model, the 2 sided two sample t-test will be used for purposes of calculating the required sample size. A sample size of 39 subjects per group will yield 80% power to detect a 2 point difference between the two groups on any single day using a two sided two-sample t-test at the 0.01 significance level. The reason for applying this “Bonferroni-type” adjustment is that pairwise comparisons will be carried out for 6 different days, and with this number of statistical tests, it is more likely to find a significant difference at the nominal 5% level when one does not actually exist. Based on our experience, most, if not all patients return for the postoperative visit, and therefore, no adjustment for drop-out has been made. Therefore, the proposed sample size will be 78 subjects (39 for each treatment group). |

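### The primary RMANOVA has no prespecified method for missed survey days, and the 78 patients that section 8 presents as covering losses contain no meaningful reserve

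*Combined protocol and SAP*

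**What the plan says.** **Sample size.** Section 12 (Sample Size Justification) derives 39 per group from a two-sided two-sample t-test at 0.01, a 2-point difference, SD 2.5 and 80% power. It then states "Based on our experience, most, if not all patients return for the postoperative visit, and therefore, no adjustment for drop-out has been made" and arrives at 78. Section 8 describes the same number differently: "We will enroll 78 patients in the event that we lose some to follow up or if patients decide to unenroll in the study". It expects few losses because "The historic rate of patient's not following up with the surgeons after ACL reconstruction is almost 0".

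**Data collection.** Section 12 (Primary Outcome): "Outcomes for days 0, 1,2,3,4, and 7 will be obtained via email and electronic surveys". Only the last assessment, labelled Day 10, is tied there to the office visit. The section 4 primary endpoint lists no day 0. Sections 10 and 11 also describe a survey sent on day 14.

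**Analysis.** For the primary outcomes, section 12 specifies: "For each outcome, repeated measures analysis of variance (RMANOVA), where post-operative pain control method (bolus block, continuous catheter) is the between subjects effect". Day is the within-subject effect, and the model also contains site and the treatment-by-day interaction. Tests at single days are conditional: "If the interaction is significant, then pairwise comparisons of pain control method at each day will be carried out within the RMANOVA model". A transformation or a non-parametric method is the fallback. The intention-to-treat paragraph says "The ITT population will be all subjects randomized, regardless of what treatment they actually received".

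**Missed days and withdrawal.** Section 16 says that a single unreachable day is not a loss to follow-up and will be documented and taken into account at analysis, without naming a method. It keeps withdrawn patients in their randomised group, with a note for post-hoc analysis. Early in the section, participants who withdraw from a study arm are still contacted, surveys included, unless they decline. Later, patients who cannot be contacted are withdrawn from study participation.

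**The concern.** Sections 8 and 12 cannot both be right about what 78 contains. A reader of section 8 would credit the design with a reserve that the calculation did not build in.

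The reason given for zero loss concerns attendance at an office visit. The comparison being sized is on any single day, and most of those days are collected by email survey. A patient can attend the visit and still have missed day 3.

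The larger gap is in the analysis. RMANOVA in its classical form needs a complete set of days and drops any patient with a missed one. That would sit badly with an analysis population of all randomised patients. Intention to treat says who is analysed and in which group; it does not say what happens to a missing value. The handling of missed days is therefore not prespecified in this document, in an open-label trial with patient-reported primary outcomes.

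**Working it through.** **Inputs from section 12:** difference 2, SD 2.5, two-sided alpha 0.01, 39 per arm, 1:1 allocation.

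**1. Reproduce the stated figure.** Standardised difference d = 2/2.5 = 0.8. With n per arm, the t-test has 2n − 2 degrees of freedom and noncentrality d·√(n/2). At n = 39: df = 76, noncentrality 0.8·√19.5 = 3.533, critical value 2.642.

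- n = 39: power 81.0%
- n = 38: power 79.75%
- exactly 80% at n = 38.19

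So 39 is the smallest whole number that reaches 80%, and the stated size is correct on its own inputs. The tolerable missing fraction is 1 − 38.19/39 = 2.1%.

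**2. All available records used.** The documents give no completion rate, so m = 2% and m = 5% missing per survey are assumptions. Records per arm on a given day = 39(1 − m).

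- m = 2%: 38.22 per arm, power 80.0%
- m = 5%: 37.05 per arm, power 78.5%

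**3. Patients with any missed survey dropped (not established by the text).** With independent misses over k occasions, complete patients per arm = 39(1 − m)^k. The documents support k = 5 (section 4, no day 0), k = 6 (section 12), or k = 7 if day 0 is included and the last assessment can also be missed.

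| m | k | Complete per arm | Patients dropped of 78 | Power |
|---|---|---|---|---|
| 5% | 5 | 30.18 | 17.6 | 67.1% |
| 5% | 6 | 28.67 | 20.7 | 64.1% |
| 5% | 7 | 27.2 | 23.5 | 61.1% |
| 2% | 5 | 35.25 | 7.5 | 75.8% |
| 2% | 6 | 34.55 | 8.9 | 74.8% |
| 2% | 7 | 33.9 | 10.3 | 73.6% |

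**4. Clustered misses under the same deletion rule.** If all misses fall in the same patients, m = 5% removes 78 × 0.05 = 3.9 patients and power is 78.5%, as in step 2. Partial clustering lies between this and step 3.

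All of these figures concern the single-day contrast at 0.01. None is the power of the RMANOVA treatment or interaction test.

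**The case against.** The plan takes real steps against missing surveys. Section 6 provides reminders every two hours and staff contact, and section 7 requires a working telephone and email access. If missingness is near 2% and all records are used, power stays at about 80%. This stands: on available records the loss is small.

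Three stronger readings are tempting and are not supported.

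- *That patients with a missed survey will be dropped, so power falls to 61–67%.* The plan never says so. The intention-to-treat paragraph and the section 16 remark about taking a one-day miss into account both point away from it. The range also needs an assumed 5% rate and independent misses.
- *That the method will be picked once results are known.* Section 16 defers the matter to the analysis phase and uses the term post-hoc for its notes on deviations and withdrawals. Neither says that the data will be inspected first. What can be said is that no method is prespecified here.
- *That the plan is silent on surveys after withdrawal.* Section 16 does provide for continued contact, including surveys. The difficulty is that its later text withdraws uncontactable patients from participation, so the two need reconciling.

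It can also be said that one sentence committing to all available days would be enough. That would close the main gap, but only with a model that can use incomplete patients, so the model needs naming too.

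**Conclusion.** The concern holds in two parts. The more important is that the primary RMANOVA has no prespecified method for missed days. The other is that sections 8 and 12 contradict each other on what 78 contains; the arithmetic agrees with section 12, and 78 holds no meaningful reserve (81.0% at 39 per arm against 79.75% at 38).

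The certain cost is small: about 1 to 2.5 percentage points of single-day power at an assumed 2% to 5% missing, if all records are used. A large loss is conditional on a deletion rule that the text leaves possible but does not adopt. The sample size calculation itself is not in error. This should be fixed before analysis, chiefly because the remedy is cheap and removes the dependence on an unstated rule.

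**What to change.** 1. **Section 12, Primary Outcomes.** For maximum pain, current pain and daily opioid consumption, replace RMANOVA with a likelihood-based mixed model for repeated measures (treatment, day, treatment-by-day, site). It should use every available post-operative value from all randomised patients. State the missing-at-random assumption and report by arm the number with no post-operative value. Specify one sensitivity analysis that works for both pain and opioid outcomes, for example multiple imputation with missed values shifted in the unfavourable direction. Say how missed days are treated if the non-parametric fallback is used. The covariance structure and degrees-of-freedom method can be left to the trial statistician.
2. **Sections 8 and 12, sample size.** State in section 8 that 78 contains no allowance for losses. In section 12, replace the visit-attendance argument with an assumed survey completion rate and restate single-day power at that rate (for example 78.5% at 5% missing), keeping 78.
3. **Section 16.** Refer to the method in item 1 for missed days. Reconcile continued contact after withdrawal with the withdrawal of uncontactable patients, so that it is clear whether surveys continue.
4. **Sections 10, 11 and 12.** Reconcile whether the last assessment is a day-14 survey or the office visit.

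The cost is wording only. Stated power may fall slightly below 80%, and the mixed model relies on missing at random, which the data cannot confirm; the sensitivity analysis is there for that reason.

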13. SPECIMEN BANKING

- *If specimens will be banked for future research, describe where the specimens will be stored, how long they will be stored, how they will be accessed and who will have access to the specimens*
- *List the information that will be stored with each specimen, including how specimens are labeled/coded*
- *Describe the procedures to release the specimens, including: the process to request release, approvals required for release, who can obtain the specimens, and the information to be provided with the specimens.*

n/a

14. DATA MANAGEMENT AND CONFIDENTIALITY

- *Describe the data and specimens to be sent out or received. As applicable, describe:*
 - *What information will be included in that data or associated with the specimens?*
 - *Where and how data and specimens will be stored?*
 - *How long the data will be stored?*
 - *Who will have access to the data?*
 - *Who is responsible for receipt or transmission of data and specimens?*
- *Describe the steps that will be taken to secure the data during storage, use and transmission.*

There will be no data in regard to specimens in this study.

All recorded data with respect to the questions listed above will be recorded onto a data sheet on the Northwell REDCap software to ensure patient confidentiality and encryption. Only investigators and co investigators will have access to the REDCap file which will be secured by password. Once the data has been analyzed the patient specific information will be deleted.

15. DATA AND SAFETY MONITORING PLAN

A specific data and safety monitoring plan is only required for greater than minimal risk research. For guidance on creating this plan, please see the [Guidance Document](#) on the HRPP website.

*Part I – this part should be completed for all studies that require a DSMP.
 Part II – This part should be completed when your study needs a Data and Safety Monitoring Board or Committee (DSMB/C) as part of your Data and Safety Monitoring Plan.*

Part I: Elements of the Data and Safety Monitoring Plan

- *Indicate who will perform the data and safety monitoring for this study.*
- *Justify your choice of monitor, in terms of assessed risk to the research subject's health and well being. In studies where the monitor is independent of the study staff, indicate the individual's credentials, relationship to the PI, and rationale for selection*
- *List the specific items that will be monitored for safety (e.g. adverse events, protocol compliance, etc)*
- *Indicate the frequency at which accumulated safety and data information (items listed in # above) will be reviewed by the monitor (s) or the DSMB/C.*
- *Where applicable, describe rules which will guide interruption or alteration of the study design.*
- *Where applicable, indicate dose selection procedures that will be used to minimize toxicity.*
- *Should a temporary or permanent suspension of your study occur, in addition to the IRB, indicate to whom will you report the occurrence.*

DSMP form is attached

Part II: Data and Safety Monitoring Board or Committee

- *When appropriate, attach a description of the DSMB.*
- *Provide the number of members and area of professional expertise.*
- *Provide confirmation that the members of the board are all independent of the study.*

n/a

16. WITHDRAWAL OF SUBJECTS

- *Describe anticipated circumstances under which subjects will be withdrawn from the research without their consent*
- *Describe procedures for orderly termination*
- *Describe procedures that will be followed when subjects withdraw from the research, including partial withdrawal from procedures with continued data collection.*

Participants may withdraw voluntarily from the study at any given time with no reason as is outlined in the informed consent for participation in the study. Any participant who withdraws from a study arm will still be contacted for follow-up assessments as outlined within this protocol unless the participant elects to forgo follow-up contact with the study assessors. This will include the surveys for outcome assessment, phone calls made on the subsequent postoperative days and the office visit following surgery.

Discontinuation from the continuous administration of local anesthetic prior to completion of the medications' dosing will not be deemed a withdrawal from the study but rather a discontinuation of treatment and the participant will continue to be followed up with for assessment of study outcomes with notation of the discontinuation of treatment within the database and the reason for discontinuation documented.

All participants who discontinue intervention will be followed in order to assess for potential adverse events, serious adverse events and any unanticipated problems pertaining to the use or administration of the study medications.

Adverse events include but are not limited to block failure, allergy to local anesthetic, persistent pain at injection/catheter site, local skin irritation at catheter site, pump/device failure.

Should a participant experience any of the serious adverse events listed in the next section, this participant will immediately be halted from their study intervention. These patients will be recommended to seek immediate care for assessment of their serious adverse event to best ensure patient safety. Should a patient experience an adverse event or unanticipated event, the study investigator who is contacted will determine if the participant's event meets criteria for discontinuation of treatment.

ADVERSE EFFECTS OF TREATMENT

Risks associated with single shot adductor canal block

1. Peripheral Nerve Injury
 - a. This is a rare complication that is usually transient and goes away with time. The estimated incidence is .5% for any nerve irritation after the procedure. The risk of injury to the nerve that is permanent in 1/10,000. These are very rare in part due to the implementation and success of ultrasound use for guidance of the needle and/or catheter during nerve blockade. This allows the anesthesiologist direct visualization to differentiate between perineural, intraneural, and interfascicular.
 - b. These injuries will be monitored with a physical examination after the procedure once the patient has woken from anesthesia. Any deficits beyond what is expected by the nerve blockade will be followed at post-operative visit in the office to evaluate for resolution of transient symptoms. In the event of a peripheral nerve injury there is no intervention that can change the outcome of the block that has been delivered. If symptoms fail to progressively improve, neurological consultation should be sought in 3-4 weeks. Incomplete lesions with evidence of moderate or severe deficit are an indication for early neurological consultation and consideration of neurophysiologic testing (nerve conduction studies and electromyography).
2. Local Anesthetic System Toxicity
 - a. Ranges from mild symptoms of metallic taste, agitation, and circumoral numbness to more severe findings such as seizure, respiratory arrest, cardiac arrhythmias.
 - b. Manifestations of local anesthetic toxicity typically appear 1 to 5 minutes after the injection, but onset may range from 30 seconds to as long as 60 minutes. These symptoms will be monitored for and usually happen because of accidental injection into the vascular system. This is exceedingly rare with the advent of ultrasound

guidance and direct visualization of the injection. During the procedure the patients are attached to full monitors which will monitor blood pressure, cardiac rhythm, oxygen saturation. Any noticeable severe findings are treated with supportive care with propofol, lipid infusions which can reverse the effects from the local anesthesia.

- c. Lipid infusion protocol as recommended by the ASEA practice advisory on local anesthetic systemic toxicity is as follows:
 - i. 1.5 ml kg⁻¹ bolus of 20% lipid emulsion Infusion at 0.25 ml kg⁻¹ per min for at least 10 min after return of circulatory stability Consider giving a second bolus and increasing infusion to 0.50 ml kg⁻¹ if circulatory stability not attained Upper limit of lipid emulsion recommended is 10 ml kg⁻¹ over the first 30 min.
- d. In addition, the patients will be on a monitor in the post anesthesia recovery unit until they are deemed stable and ready for discharge. Any abnormalities will be noted by the nurse taking care of the patient who would inform the anesthesiologist and surgeon. This is standard protocol at our institution when any regional blocks are given for post-operative patients.
- e. The patients will be given a hand out and instructed to watch for signs or symptoms such as chest pain, rapid heart beating, difficulty breathing, or seizure like activity. If any of these symptoms are present, they would normally be observed immediately after the block is performed or while the patient is still being monitored, however after discharge they will still be informed to watch for symptoms in the event of a delayed response. They will be instructed to call the study PI or safety officer and likely be sent to the emergency room for evaluation.

3. Local Infection

- a. For single shot adductor canal blocks the risk of infection is very low. To minimize this risk the site is prepped in sterile fashion with either chlorhexidine or iodine scrub. The injecting physician washes hands and uses sterile gloves and instruments for the course of this procedure.
- b. Perioperative antibiotics will also be given which is standard protocol for ACL reconstruction regardless of catheter insertion or not.
- c. In the event that the patient notices any skin irritation, redness, foul smell, or drainage form the site of the injection, they will be advised to first call the safety officer, PI, or other co-investigator to describe their symptoms. The patients will also watch for fevers or chills. If infection is suspected they will be sent to the emergency room or surgeons office for evaluation and further testing. They may be started on a course of oral antibiotics if an infection is concerning after evaluation.

Risks associated with continuous peripheral nerve catheter placement:

1. Both anesthetists and surgeons recognize the benefits of peripheral nerve catheters (PNCs). The continuous infusion of local anesthetic near a peripheral nerve or plexus produces fewer systemic side-effects than i.v. opioids, increases postoperative patient satisfaction, and can allow for faster functional recovery of the operated limb.
2. Block Failure
 - a. Occasionally, there are instances when the catheter is passed easily but the nerve block fails to provide adequate anesthesia or analgesia.
 - b. This is rare with the use of ultrasound guidance and localization of the continuous catheter.
 - c. In the event of a block failure or inadequate placement that is not providing the patient any relief, the catheter will be removed either by the patient or post operatively depending on when it is discovered.
 - d. The practicing anesthesiologist will discuss with the patient the option of either trying a second time to place the catheter successfully in the post anesthesia recovery area or discontinuing the block altogether.
3. Accidental Catheter Migration/Removal
 - a. The incidence of accidental catheter removal is reported in the literature at about 1%. The use of sterile adhesive tagaderm dressing has been implemented to firmly secure the catheter to the skin to avoid migration or fall out. The dressing is checked to be secure after it has been applied.
 - b. In the event that the catheter is accidentally removed or dislodged during the course of the study, it should be removed and there will be no further intervention once the patient has been discharged home. The patient can place a Band-Aid over the catheter site and notify the coinvestigator or PI.
4. Localized Infection
 - a. Localized inflammation is infrequent (0–10%), and local infection (0–3%), abscess formation (0–0.9%), and sepsis occur even more rarely.
 - b. Transparent dressings are used to reduce the number of dressing changes while appropriately monitoring the site for signs of inflammation
 - c. Since the continuous catheter remains in for 48-72 hours, it does pose a theoretical increased risk of infection compared to a single shot adductor canal block although this has not been proven in the literature. To minimize this risk the site is prepped in sterile fashion with either chlorhexidine or iodine scrub. The injecting physician washes hands and uses sterile gloves and instruments for the course of this procedure.

- d. Perioperative antibiotics will also be given which is standard protocol for ACL reconstruction regardless of catheter insertion or not.
- e. In the event that the patient notices any skin irritation, redness, foul smell, or drainage from the site of the injection, they will be advised to first call the safety officer, PI, or other co-investigator to describe their symptoms. The patients will also watch for fevers or chills. If infection is suspected they will be sent to the emergency room or surgeon's office for evaluation and further testing. They may be started on a course of oral antibiotics if an infection is concerning after evaluation

5. Local Anesthetic System Toxicity

- a. The patients with a continuous catheter will be receiving a fixed rate of flow of local anesthetic to the nerve site for 48-72 hours. This does put them at a theoretical risk for toxicity while they are at home with the catheter in even though the dosage is well below the threshold for systemic toxicity. They will be educated on the following signs and symptoms similar to the single shot patients.
- b. Ranges from mild symptoms of metallic taste, agitation, and circumoral numbness to more severe findings such as seizure, respiratory arrest, cardiac arrhythmias.
- c. Manifestations of local anesthetic toxicity typically appear 1 to 5 minutes after the injection, but onset may range from 30 seconds to as long as 60 minutes. These symptoms will be monitored for and usually happen because of accidental injection into the vascular system. This is exceedingly rare with the advent of ultrasound guidance and direct visualization of the injection. During the procedure the patients are attached to full monitors which will monitor blood pressure, cardiac rhythm, oxygen saturation. Any noticeable severe findings are treated with supportive care with propofol, lipid infusions which can reverse the effects from the local anesthesia.
- d. Lipid infusion protocol as recommended by the ASEA practice advisory on local anesthetic systemic toxicity is as follows:
 - i. 1.5 ml kg⁻¹ bolus of 20% lipid emulsion Infusion at 0.25 ml kg⁻¹ per min for at least 10 min after return of circulatory stability Consider giving a second bolus and increasing infusion to 0.50 ml kg⁻¹ if circulatory stability not attained Upper limit of lipid emulsion recommended is 10 ml kg⁻¹ over the first 30 min.
- e. In addition, the patients will be on a monitor in the post anesthesia recovery unit until they are deemed stable and ready for discharge. Any abnormalities will be noted by the nurse taking care of the patient who would inform the anesthesiologist

and surgeon. This is standard protocol at our institution when any regional blocks are given for post-operative patients.

- f. The patients will be given a hand out and instructed to watch for signs or symptoms such as chest pain, rapid heart beating, difficulty breathing, or seizure like activity. If any of these symptoms are present, they would normally be observed immediately after the block is performed or while the patient is still being monitored, however after discharge they will still be informed to watch for symptoms in the event of a delayed response. They will be instructed to call the study PI or safety officer and likely be sent to the emergency room for evaluation.

Unanticipated events will be assessed on a case by case basis and the study investigators will determine if the patient should be halted/discontinued and whether or not they should seek immediate care.

Any participant who is discontinued from treatment will continue to be assessed following the previously stated follow-up procedure.

The data to be collected at the time of study intervention discontinuation will include the following:

- All data pertaining to the patient's enrollment in the study including which arm of the study they were randomized to, whether or not they received the treatment to which they were randomized, all outcome data that was recorded up to the time of discontinuation and any stated reason for discontinuation will be documented.
- Should a participant experience a known complication of the medication this will be recorded as an adverse event, serious adverse event, or unanticipated event as noted above.
- The participants will continue to be followed according the protocol and their outcome data will continue to be obtained as is possible given the situation.
- A case report form page will be produced for any participant who discontinues treatment or withdraws, this will include the date and any specific reasons for discontinuation/withdrawal from the study.

Participants are free to withdraw from participation in the study at any time upon request.

An investigator may discontinue or withdraw a participant from the study for the following reasons:

- Serious adverse event
- Pregnancy
- Significant study intervention non-compliance

- If any clinical adverse event (AE), laboratory abnormality, or other medical condition or situation occurs such that continued participation in the study would not be in the best interest of the participant. Adverse events or unanticipated events will be assessed on a case by case basis and discontinued as noted in the section above.
- If the participant meets an exclusion criterion (either newly developed or not previously recognized) that precludes further study participation.
- An investigator will discontinue/withdraw a patient from study participation if they are not deemed contactable, this will be defined as inability to contact after 3 separate attempts are made at least 2 hours apart across two days.

The reason for participant discontinuation or withdrawal from the study will be recorded on the Case Report Form (CRF) as noted in the section above. Subjects who sign the informed consent form and are randomized but do not receive the study intervention they are randomized to will be followed in the study as if they have obtained their intervention this deviation from protocol will be documented for post-hoc analysis reasons. Subjects who sign the informed consent form, and are randomized and receive the study intervention, and subsequently withdraw, or are withdrawn or discontinued from the study, maintained in the group to which they are randomized for assessment documentation with notation made as to their withdrawal to assist in the post-hoc analysis.

Study participants who are randomized to the continuous infusion cohort will be provided with information about the pumps themselves and troubleshooting advice. They will also be provided with contact information for the investigators should they run into issues. The troubleshooting of the device will be done as noted in the above section and need for discontinuation of the therapy will be assessed as noted above with safety concerns as the primary reason for discontinuation.

A participant will be considered lost to follow-up if he or she fails to respond to study surveys followed for more than one day of follow up, misses the phone calls, or misses the post-operative office visit planned for postoperative day 10-14 and is unable to be contacted by the study site staff.

The following actions must be taken if a participant fails to respond to study surveys or return to the clinic for a required study visit:

